Aim 1: The primary outcome is weaning duration. Sample size has been determined to adequately power 3 separate comparative analyses: (a) REDvent-acute versus Acute Phase control (b) REDvent-weaning phase versus Weaning Phase control (c) REDvent both phases versus control both phases. Power is based on 2 planned methods for analysis: cox proportional hazard ratios for multivariable analysis and univariate analysis with an independent t-test using log transformation (as needed) to account for the expected distribution of weaning duration. For all three of the planned comparisons above, with the proposed sample size we would be adequately powered (>0.8) to detect a difference in weaning duration of ≥ 1 day, or a hazard ratio of ≥ 1.4 between groups. The secondary outcomes are ventilator free days and extubation failure. Directly comparing control only patients to REDvent only patients, with an expected standard deviation for VFDs between 5 to 9 days, we will be able to detect a 2-day change in VFDs between groups with a power between 0.35 and 0.82. Re-intubation rates are expected to be 10%, allowing us to confirm that REDvent is not inferior to usual care in regards to re-intubation with a non-inferiority margin of 0.10 with a power of 0.8 and alpha of 0.05.

Aim 2: The primary outcome of this aim is weaning duration. For respiratory muscle strength we will compare the first measured aPiMax (after resolution of the acute phase, before the first SBT), the trajectory and value of the daily aPiMax during the weaning phase prior to extubation, the lowest and highest measured aPiMax, and aPiMax on the day of extubation against weaning duration. For analysis, aPiMax will be dichotomized at 30 cmH₂O, and weaning duration will be compared between patients with aPiMax > 30 versus ≤ 30 cmH₂O using a t-test with or without log-transformation, or Mann-Whitney U test, depending on the distribution. From our preliminary data, we anticipate at least 35% of patients (n=84) will have aPiMax ≤ 30 cmH₂O. Based on a similar power analysis as presented above, this would allow us to determine whether low aPiMax

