Monitoring: The study will one planned interim analysis at 150 patients, with no rules planned for early stopping, given the low risk nature of this study and the high degree of physiologic data collected. In addition, there will be an early safety check after approximately 50 patients are enrolled, to review rates of adverse events between groups. There will be review of adverse events by the DSMB during scheduled meetings twice a year, or as requested.

A3 Primary Hypothesis and Specific Aims

Our central hypothesis is that REDvent use will reduce ventilator-induced respiratory muscle weakness, leading to shorter time on MV by enhancing the patient's capacity for effective, unsupported ventilation and by facilitating MV weaning. This will be specifically tested with 3 complementary specific aims:

SA1: To determine if REDvent acute and/or weaning phase protocols can shorten the duration of weaning from MV (Primary outcome). We expect that patients randomized to receive REDvent-acute will either pass their first SBT or experience a shorter duration of weaning when compared to usual care. In addition, patients randomized to receive REDvent-weaning will experience a shorter duration of weaning compared to usual care. Secondary outcomes include 28-day Ventilator Free Days and extubation failure.

SA2: To determine if changes to direct measures of respiratory muscle strength, load, effort, and architecture throughout the duration of MV are related to weaning outcomes. We expect that diminished respiratory muscle strength (low PiMax), and diaphragm atrophy (ultrasound) will be prevalent after resolution of the acute phase of MV, and the combination of high respiratory load (or effort) with low PiMax will be a major factor leading to prolonged weaning and weaning failure (failure of SBT).

SA3: To determine if patient effort of breathing during both acute and weaning phases of MV is independently associated with the development of respiratory muscle weakness. We expect that after controlling for confounding variables like age, diagnosis, sedation, use of neuromuscular blockade, and other risk factors for neuromuscular weakness, children who maintain normal effort of breathing in the acute or weaning phases will have higher respiratory muscle capacity as measured by PiMax.

B Background

B1 Prior Literature and Studies

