Comparison (a) REDvent-acute versus control: A 1-day reduction in length of weaning is considered clinically significant (less sedative exposure, fewer nosocomial infections, lower healthcare costs). With a sample size of 276 patients (138 per arm), up to 12% mortality and 1% attrition or incorrect randomization, a minimum of 240 patients (120 per arm) will be available for analysis of the acute phase. Power is based on 2 planned methods for analysis: cox proportional hazard ratios for multivariable analysis and univariate analysis with an independent t-test using log transformation (as needed) to account for the expected distribution of weaning duration. For univariate analysis using the assumptions above, we would be able to detect a ≥ 1 -day reduction in weaning duration with an alpha of 0.05 and power of 0.9 (Figure 7). For the cox proportional hazard model, we would be able to detect a relative hazard ratio of 1.5 (ratio between control/intervention group) with a power of 0.9 or a hazard ratio of 1.4 with a power of 0.8.

Comparison (b) REDvent-weaning versus control: Patients who fail the initial SBT will undergo the weaning phase randomization. From our pilot data, approximately 25% of patients exposed to the intervention passed the initial SBT, corroborating previous studies.¹⁵ Thus, at least 180 patients (90 per arm) will receive weaning phase interventions. Using the same assumptions as above, we will be able to detect a ≥ 1 day

reduction in the length of the weaning phase (Figure 8), or a hazard ratio of 1.5 with an alpha of 0.05 and power of 0.8. Patients who do not pass the SBT by 28 days post the weaning phase randomization will be censored for analysis, as study interventions and daily monitoring will end on day 29.

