strength we will compare the first measured aPiMax (after resolution of the acute phase, before the first SBT), the trajectory and value of the daily aPiMax during the weaning phase prior to extubation, the lowest and highest measured aPiMax, and aPiMax on the day of extubation against weaning duration. For analysis, aPiMax will be dichotomized at 30 cmH₂O (based on our preliminary data), and weaning duration will be compared between patients with aPiMax > 30 versus ≤ 30 cmH₂O using a t-test with or without log-transformation, or Mann-Whitney U test, depending on the distribution. From our preliminary data, we anticipate at least 35% of patients (n=84) will have aPiMax ≤ 30 cmH₂O. Based on a similar power analysis as presented above, this would allow us to determine whether low aPiMax is associated with a ≥ 1-day increase in weaning duration, with an alpha of 0.05 and power of 0.8. We will perform identical analysis for ePiMax.

Diaphragm Thickness analysis will compound daily ultrasound measures to detect the relative change in diaphragm thickness from study day 1 until passage of an SBT. We will compare the change in thickness after resolution of the acute phase (on the day of the first SBT) against weaning duration, in a similar manner as proposed above for aPiMax. For analysis, diaphragm thickness will be tested as a continuous variable (with Spearman's or Pearson's Correlation), but also categorized into 3 groups (loss of > 10% in thickness, maintenance of thickness (-10% to +10%), and increase in size of > 10%) to account for the potential ill effects of diaphragm hypertrophy (expected in about 10% of patients), using Analysis of Variance (ANOVA) to compare weaning duration between groups. We will characterize how diaphragm thickness changes daily during the weaning phase compared to the thickness on study day 1, as well as the daily thickness compared to that on the day of the first SBT. This will be used to determine whether patients whose trajectory of diaphragm atrophy continues during the weaning phase have a longer weaning duration compared to those who maintain diaphragm thickness or have increased thickness during the weaning phase. We anticipate high correlation between aPiMax and diaphragm atrophy, such that the proportion of patients with > 10% loss in diaphragm thickness will be similar to the proportion of those with aPiMax ≤ 30 cmH₂O, resulting in the same sample size that yield adequate power, as above.

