retain an independent association with SBT failure. Because SBTs will be repeated daily, we will use a hierarchical logistic regression model to control for repeated measures from each patient as well as controlling for the other potential confounding variables detailed in the data collection table. We anticipate that 240 patients will undergo SBT testing, and 90% of these patients will pass the SBT within 28 days of the weaning phase randomization. As such, we would be able to include at least 20 variables in a multivariable hierarchical logistic regression model. Finally, we will determine whether common “phenotypes” for weaning failure can be determined. We anticipate four possible phenotypes by combining information from all available measures of capacity, load, effort, and architecture. Based on our preliminary data, we anticipate that patients with high load will be more likely to fail weaning, but that this effect will be more pronounced if they have diminished respiratory muscle capacity. We hypothesize that the rates of passage of the SBT will increase incrementally from phenotype 1 to 4: (1) Diminished capacity, high load and effort; (2) Normal capacity, high load and effort; (3) Diminished capacity, low load and effort; (4) Normal capacity, low load and effort. These phenotypes are exploratory; thus, no power analysis is provided.

D.6.4.3 SA3 Analysis Plan: To determine if patient effort of breathing during both acute and weaning phases of MV is independently associated with the development of respiratory muscle weakness.

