The analytic approach for secondary aims and outcomes such as mortality and ventilator free days will follow those described above. For categorical data, a χ^2 or Fisher's exact test will be used to compare difference between groups. Logistic regression will be used to assess binary outcomes, and a multinomial/ordinal logistic regression will be used for categorical outcomes (> 2 categories) while adjusting for covariates. To assess the association between 2 continuous variables, a Pearson or Spearman correlation will be used, and analysis of covariance (ANCOVA) will be used to adjust for covariates. Generalized Estimating Equations (GEE) or mixed effect models will be used when necessary to analyze repeated measures. Because of the physiologic nature of the study with a Phase II design,

multiple comparisons adjustment is not planned for secondary outcomes. Analyses will be performed using the appropriate recent version of the SAS statistical software (SAS Institute Inc., Cary, NC).

In order to increase precision around the effect estimates for the primary and secondary aims and to reflect the stratified sampling, all analyses are adjusted for block randomization variables.³ For acute phase these are age group (infant, child, and adolescent) and whether or not the subject was immunocompromised. For the weaning phase this is acute phase randomization grouping and age group. In addition, variables thought to be potential confounders on the relationship between intervention and outcome with large differences between groups (standardized effect sizes as detailed above) will also be included in all adjusted analyses. Unadjusted analyses will be presented to summarize data; all primary and secondary outcomes will present adjusted analyses controlling for age category, immunosuppression and imbalanced baseline variables. Potential confounders will be assessed for multicollinearity and if present, the confounder with the highest biological plausibility to impact the effect of the intervention on the outcome will be selected for inclusion as a model covariate.

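### Aim 2 compares weaning duration by aPiMax with both arms pooled and no arm term, so any REDvent effect on weaning that bypasses strength would be counted as a strength–weaning association

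*Combined protocol and SAP*

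**What the plan says.** Protocol section D.6.4.2 (SA2 Analysis Plan) takes weaning duration as the outcome of Aim 2 and splits children at an aPiMax of 30 cmH₂O: "weaning duration will be compared between patients with aPiMax > 30 versus ≤ 30 cmH₂O using a t-test". The alternatives, chosen by distribution, are a t-test on the log scale and a Mann-Whitney test. The Aim 2 summary in A2 says the same, and the 276-patient protocol keeps the text. The sample is both arms together: "we anticipate at least 35% of patients (n=84) will have aPiMax ≤ 30 cmH₂O". The planned conclusion is whether "low aPiMax is associated with a ≥ 1-day increase in weaning duration, with an alpha of 0.05 and power of 0.8". ePiMax is to be analysed identically, and diaphragm thickness, load and effort in a similar way.

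On the expected action of REDvent, A3 says that it will reduce muscle weakness and shorten ventilation "by enhancing the patient's capacity for effective, unsupported ventilation and by facilitating MV weaning". D.6.2 adds that acute-phase management may have a lasting effect on strength that carries into weaning, and it blocks the weaning randomisation by acute-phase group.

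On adjustment, within Aim 2 a model with covariates is written only for the secondary outcome of SBT failure, "controlling for the other potential confounding variables detailed in the data collection table". That table does not list the randomised arm. The July 2024 SAP has a general rule that analyses are adjusted for the blocking variables: "For acute phase these are age group (infant, child, and adolescent) and whether or not the subject was immunocompromised". For the weaning phase it names the acute-phase group and age. The same paragraph ends by naming the adjusted set for all primary and secondary outcomes as age, immune status and unbalanced baseline variables, without the arm. The Fall 2019 SAP has the same rule.

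**The concern.** The acute-phase arm is a potential common cause of the exposure (aPiMax at the first SBT) and the outcome (weaning duration). If REDvent preserves strength, usual-care children are over-represented in the weak group. If REDvent also shortens weaning by some other route, those children wean more slowly for reasons unrelated to strength, and a pooled two-group test attributes that delay to weakness.

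Aim 2 is the trial's link between weakness and prolonged weaning. The distortion is absent when REDvent does nothing and grows as REDvent works better, so it would be largest when the mechanism is of most interest for a Phase III trial.

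**Working it through.** **Inputs.** D.6.4.1, comparison (a): "a minimum of 240 patients (120 per arm) will be available for analysis of the acute phase". Low aPiMax: 35% of 240 = 84, leaving 156. SDs from D.6.4.1: 2.8 days (historical controls) and 2.1 days (REDvent pilot). Design effect: 1 day. Alpha 0.05, two-sided (stated for the primary outcome, assumed here). Low-aPiMax rates by arm are **not given**, so I assume three pairs that keep the overall rate at 35%.

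**The plan's own power.** SE = √(2.8²/84 + 2.1²/156) = √(0.0933 + 0.0283) = 0.349. Power = Φ(1/0.349 − 1.96) = Φ(0.91) = 0.82. With the pooled SD of 2.475, SE = 2.475 × √(1/84 + 1/156) = 0.335 and power = 0.85. The stated 0.8 is reproduced.

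**Spurious difference.** Suppose aPiMax has no effect within either arm and REDvent shortens weaning by D days without going through strength. The expected weak-minus-strong difference is then

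D × [P(usual care | weak) − P(usual care | strong)].

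The false-positive rate is Φ(b/SE − 1.96) + Φ(−b/SE − 1.96), where b is the spurious difference. Each group's variance is f × 2.8² + (1 − f) × 2.1² + D² × f(1 − f), with f the usual-care share of that group. For D = 1:

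| Low aPiMax, usual care/REDvent | Usual-care share, weak | Usual-care share, strong | Spurious difference | SE | False-positive rate |
|---|---|---|---|---|---|
| 40/30% | 48/84 = 0.571 | 72/156 = 0.462 | 0.11 day | 0.345 | 6.2% |
| 45/25% | 54/84 = 0.643 | 66/156 = 0.423 | 0.22 day | 0.347 | 9.7% |
| 50/20% | 60/84 = 0.714 | 60/156 = 0.385 | 0.33 day | 0.350 | 15.6% |

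Simulation with skewed (gamma) durations gives t-test rates of 6%, 10% and 17%, and 5–6% with the arm in the model. With equal rates (35/35%) the shares are equal, the difference is zero, and the simulated rate is about 4%.

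**Power with the arm in the model.** SE = 2.475/√w, where w = 120 × [p₁(1 − p₁) + p₂(1 − p₂)].

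- 40/30%: w = 54.0, power 0.84.
- 45/25%: w = 52.2, SE 0.343, power 0.83, against 0.85 unadjusted. Simulation with arm-specific SDs and robust standard errors gives 0.81.
- 50/20%: w = 49.2, power 0.81. With arm-specific SDs, SE = √(30 × 7.84 + 19.2 × 4.41)/49.2 = 0.364 and power = Φ(0.79) = 0.79.

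**The case against.** The strongest reply is that the SAP already covers this. It says that analyses for the primary and secondary aims are adjusted for blocking variables, shows unadjusted results only as summaries, offers ANCOVA for associations, and names the acute-phase group among the weaning-phase blocking variables. Table 1 is organised by outcome, and its first row, length of weaning, is adjusted for blocking variables and confounders. A reader who infers that the plan is wholly unadjusted therefore goes further than the documents allow. What stands is that the rule never mentions Aim 2 or says which blocking set applies to it, and its closing list leaves out the arm. The first aPiMax is taken before weaning randomisation, and the outcome includes children who are never randomised for weaning. An analyst could follow D.6.4.2 literally or add the arm, and either would be defensible.

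A second reply is that the routes need not be separate. Both clauses of the A3 hypothesis can be read as consequences of reduced weakness, and the path in D.6.2 runs through strength. That is fair, and the calculation is a worst case for this reason. However, the asynchrony section (H, Specific Aim 2) expects REDvent to shorten ventilation through lung protection as well as less diaphragm injury, so a route outside strength is not foreign to the documents.

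Two further inferences are not supported. A reader might apply the pilot's 1.8-day difference (4 − 2.2) to the table, which at 50/20% gives 0.59 day and a false-positive rate near 37%. That effect came from REDvent in both phases, and comparison (c) expects 90 of the 240 children to have mixed treatment, so it does not belong to the 120/120 acute-arm split. A reader might also infer that the result will be presented as proof that weakness prolongs weaning. D.6.4.2 claims only an association, although SA2 in A3 does expect low PiMax combined with high load to be a major factor in prolonged weaning.

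**Conclusion.** The point holds as an under-specified adjustment in Aim 2: the stated test has no arm term, and no other passage clearly supplies one. With a 1.0-day effect, the false-positive rate would be about 6%, 10% or 17% and the average spurious difference about 0.1, 0.2 or 0.3 day. These sizes rest on assumed low-aPiMax rates by arm and on the whole REDvent effect bypassing strength. A smaller bypass or more similar rates would shrink them, and at 40/30% the error is close to nominal. In every one of these scenarios the average spurious difference stays well below Aim 2's 1-day target.

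No stated sample size or power figure is shown to be wrong, and the primary comparison of the arms is not affected. If REDvent acts wholly through strength the pooled association is not spurious, but the pooled test cannot tell that case from the other.

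**What to change.** In D.6.4.2 and the SAP, state that Aim 2 models weaning duration on aPiMax, by regression or a stratified rank test, with acute-phase arm, age group and immunosuppression as covariates. Apply the same to ePiMax, diaphragm thickness and the load and effort measures, and add the acute-phase arm to the hierarchical SBT-failure model.

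Add the weaning-phase arm only in analyses confined to children or SBTs after weaning randomisation. Having no weaning arm is itself a result of the first SBT, so using that arm across all children would condition on part of the outcome. For the first aPiMax, measured before that randomisation, only the acute-phase arm can confound.

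The cost is a sentence in each document and one extra model term for the arm, with no new data. About 2 points of power are lost at 45/25% (0.85 to 0.83). The stated 0.8 is kept at 240 patients, to rounding in the 50/20% case (0.79 to 0.81). The section H asynchrony plan already puts REDvent group and mediator in one model, so this is consistent with the trial's own practice.

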capacity (aPiMax > 30 cmH₂O) could tolerate moderate to high levels of load after extubation (PRP 500-1000), and re-intubation rates did not exceed the population average unless effort was very high (PRP > 1000). Post-extubation subglottic UAO was the most common reason for high respiratory muscle load after extubation, and when children with diminished respiratory muscle capacity (aPiMax ≤ 30 cmH₂O) had subglottic UAO after extubation, their re-intubation rates were 5.7 times higher than the population average (47.5% vs. 8.3%, Figure 4). The rate of aPiMax ≤ 30 cmH₂O was slightly higher for neonates (47%) compared to the other age groups, although this was not statistically significant (p=0.12; 30% infants (1-24 months), 30% child age (2-11 years) and 34% adolescents (11-18 years)). Multivariable risk factors for re-intubation include primary intubation for neurologic disease, lower aPiMax, UAO post-extubation, higher PEEP before extubation, higher PRP after extubation, and lower height (AUC 0.823). This demonstrates that **respiratory muscle weakness contributes to extubation failure**, and maintaining respiratory muscle strength will likely reduce re-intubation rates even when respiratory load after extubation is high. These data further support the hypothesis that **children with respiratory muscle weakness will have more trouble weaning from MV** when respiratory load (compliance, resistance) may still be high.

B.3.6 Summary of Preliminary Data: We have demonstrated that 35% of MV children have respiratory muscle weakness at the time of extubation, making them 3 times more likely to be re-intubated, and nearly 6 times more likely to fail when respiratory load is high.^{65, 66} We have also shown that current ventilator management in children likely exacerbates the development of respiratory weakness by lowering patient

Nevertheless, combining aPiMax with measures of respiratory effort (after extubation) such as PRP better predicted re-intubation risk (AUC 0.77). For children with diminished respiratory muscle capacity (aPiMax ≤ 30 cmH₂O), re-intubation rates were always higher than the population average, and they became accelerated as effort increased (PRP > 500). Children with maintained respiratory muscle

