Comparison (a) REDvent-acute versus control: A 1-day reduction in length of weaning is considered clinically significant (less sedative exposure, fewer nosocomial infections, lower healthcare costs). With a sample size of 300 patients (150 per arm), up to 13% mortality and 7% attrition or incorrect randomization, a minimum of 240 patients (120 per arm) will be available for analysis of the acute phase. Power is based on 2 planned methods for analysis: cox proportional hazard ratios for multivariable analysis and univariate analysis with an independent t-test using log transformation (as needed) to account for the expected distribution of weaning duration. For univariate analysis using the assumptions above, we would be able to detect a ≥ 1 -day reduction in weaning duration with an alpha of 0.05 and power of 0.9 (Figure 7). For the cox proportional hazard model, we would be able to detect a relative hazard ratio of 1.5 (ratio between control/intervention group) with a power of 0.9 or a hazard ratio of 1.4 with a power of 0.8.

Comparison (b) REDvent-weaning versus control: Patients who fail the initial SBT will undergo the weaning phase randomization. From our pilot data, approximately 25% of patients exposed to the intervention passed the initial SBT, corroborating previous studies.¹⁵ Thus, at least 180 patients (90 per arm) will receive weaning phase interventions. Using the same assumptions as above, we will be able to detect a ≥ 1 day reduction in the length of the weaning phase (Figure 8), or a hazard ratio of 1.5 with an alpha of 0.05 and power of 0.8. Patients who do not pass the SBT by 28 days post the

weaning phase randomization will be censored for analysis, as study interventions and daily monitoring will end on day 29.

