phase prior to extubation, the lowest and highest measured aPiMax, and aPiMax on the day of extubation against weaning duration. For analysis, aPiMax will be dichotomized at 30 cmH₂O (based on our preliminary data), and weaning duration will be compared between patients with aPiMax > 30 versus ≤ 30 cmH₂O using a t-test with or without log-transformation, or Mann-Whitney U test, depending on the distribution. From our preliminary data, we anticipate at least 35% of patients (n=84) will have aPiMax ≤ 30 cmH₂O. Based on a similar power analysis as presented above, this would allow us to determine whether low aPiMax is associated with a ≥ 1-day increase in weaning duration, with an alpha of 0.05 and power of 0.8. We will perform identical analysis for ePiMax.

Diaphragm Thickness analysis will compound daily ultrasound measures to detect the relative change in diaphragm thickness from study day 1 until passage of an SBT. We will compare the change in thickness after resolution of the acute phase (on the day of the first SBT) against weaning duration, in a similar manner as proposed above for aPiMax. For analysis, diaphragm thickness will be tested as a continuous variable (with Spearman's or Pearson's Correlation), but also categorized into 3 groups (loss of > 10% in thickness, maintenance of thickness (-10% to +10%), and increase in size of > 10%) to account for the potential ill effects of diaphragm hypertrophy (expected in about 10% of patients), using Analysis of Variance (ANOVA) to compare weaning duration between groups. We will characterize how diaphragm thickness changes daily during the weaning phase compared to the thickness on study day 1, as well as the daily thickness compared to that on the day of the first SBT. This will be used to determine whether patients whose trajectory of diaphragm atrophy continues during the weaning phase have a longer weaning duration compared to those who maintain diaphragm thickness or have increased thickness during the weaning phase. We anticipate high correlation between aPiMax and diaphragm atrophy, such that the proportion of patients with > 10% loss in diaphragm thickness will be similar to the proportion of those with aPiMax ≤ 30 cmH₂O, resulting in the same sample size that yield adequate power, as above.

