each patient as well as controlling for the other potential confounding variables detailed in the data collection table. We anticipate that 240 patients will undergo SBT testing, and 90% of these patients will pass the SBT within 28 days of the weaning phase randomization. As such, we would be able to include at least 20 variables in a multivariable hierarchical logistic regression model. Finally, we will determine whether common “phenotypes” for weaning failure can be determined. We anticipate four possible phenotypes by combining information from all available measures of capacity, load, effort, and architecture. Based on our preliminary data, we anticipate that patients with high load will be more likely to fail weaning, but that this effect will be more pronounced if they have diminished respiratory muscle capacity. We hypothesize that the rates of passage of the SBT will increase incrementally from phenotype 1 to 4: (1) Diminished capacity, high load and effort; (2) Normal capacity, high load and effort; (3) Diminished capacity, low load and effort; (4) Normal capacity, low load and effort. These phenotypes are exploratory; thus, no power analysis is provided.

D.6.4.3 SA3 Analysis Plan: To determine if patient effort of breathing during both acute and weaning phases of MV is independently associated with the development of respiratory muscle weakness.

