Analysis and Sample Size: The primary outcome of this aim is aPiMax < 30 cmH₂O. The analysis will focus on determining whether the degree of patient effort of breathing is independently associated with the development of respiratory muscle weakness. PRP will be the primary measure of effort of breathing, and will be measured twice daily in both acute and weaning phases. Secondary measures of effort of breathing include DCA and PTP. For the acute phase, we will generate a time- weighted average PRP during the acute phase and graph it against aPiMax at the first SBT, anticipating a positive correlation (higher average PRP values associated with higher aPiMax). We will subsequently dichotomize aPiMax at the first SBT and compare mean time weighted average PRP in the acute phase between aPiMax groups (> 30 vs. ≤ 30 cmH₂O). For the weaning phase, we will graph the changes in aPiMax throughout the weaning phase (from first failed SBT until successful SBT) against time-weighted average PRP, with the anticipation that low PRP will be associated with either further reductions in aPiMax, or no improvement, while PRP in the physiologic range of 150-400 will be associated with improvement in aPiMax. We will subsequently dichotomize aPiMax (at 30 cm H₂O) at the time of successful passage of an SBT and compare time-weighted average PRP in the weaning phase between aPiMax groups. Subsequently, we will build a multivariable logistic regression model on the outcome of aPiMax ≤ 30 cmH₂O to determine if time- weighted PRP in the acute phase, weaning phase or both have an independent association with preserving aPiMax, after controlling for confounding variables (data collection table). We anticipate that 35% of patients (at least 80) will have aPiMax ≤ 30 cmH₂O, allowing for inclusion of at least 9 variables in the multivariable model. Secondary goals are to characterize other variables that retain an independent association with low aPiMax, which are likely to include age group, use and dose of neuromuscular blockade, driving pressure during the acute phase of ventilation, sepsis, corticosteroids and use of aminoglycoside antibiotics.

D.6.5 Dissemination plan and data archiving

The results of this clinical trial will be critically important to disseminate to critical care clinicians, both pediatric and adult. In the final two years of the study the Steering Committee will develop the strategic plan for the comprehensive presentation and

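### Aim 3's 80 events and 9 variables fit only the acute-phase effort model; any model with weaning-phase effort has about 55–57 events and room for about 6 variables

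*Combined protocol and SAP*

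**What the plan says.** Section D.6.4.3 (SA3 Analysis Plan) is the same in the initial and the amended protocol. After some descriptive comparisons it plans a multivariable logistic regression with aPiMax at or below 30 cmH₂O as the outcome. The question is whether time-weighted PRP "in the acute phase, weaning phase or both have an independent association with preserving aPiMax", after adjustment for confounders. One sentence sizes the model. It starts from an expected number of events, "We anticipate that 35% of patients (at least 80) will have aPiMax ≤ 30 cmH₂O", and derives from that number how many terms the regression can carry, "allowing for inclusion of at least 9 variables in the multivariable model".

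The same section sets the weaning-phase window as running from the first failed SBT to the successful one. In the comparisons before the model, acute-phase PRP is set against aPiMax at the first SBT, and weaning-phase PRP against aPiMax at successful passage. The sentence describing the multivariable model gives no time point for aPiMax.

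The numbers of children come from elsewhere in D.6.4:

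- Comparison (a): "a minimum of 240 patients (120 per arm) will be available for analysis of the acute phase".
- Comparison (b), after about 25% pass the first SBT: "Thus, at least 180 patients (90 per arm) will receive weaning phase interventions".
- SA2, of the 240 children expected to undergo SBT testing: "90% of these patients will pass the SBT within 28 days of the weaning phase randomization".
- SA2, for the same aPiMax cut-off: "we anticipate at least 35% of patients (n=84) will have aPiMax ≤ 30 cmH₂O".

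**The concern.** One event count is offered for three possible models: acute PRP, weaning PRP, or both. Only the first can use every child who reaches an SBT. A child who passes the first SBT has no interval from a failed to a successful SBT and so no weaning-phase PRP in the Aim 3 sense. A child who never passes has no aPiMax at passage.

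Aim 3 claims an independent association, and that claim is sensitive to the number of terms relative to events. If the analysts take nine variables as the allowance for the weaning or combined model, its coefficients could be unstable and the adjusted PRP effect hard to trust. Because the time point of the multivariable outcome is not stated, the reader also cannot tell which children the count is meant to cover.

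**Working it through.** **Inputs.** 240 evaluable children (300 × 0.80 in the initial protocol; 276 × 0.87 = 240 in the amended one). 25% pass the first SBT and 180 enter weaning (Comparison (b)). The 78/72/90 split in Comparison (c) agrees: it implies first-SBT pass rates of (78 − 60)/60 = 30% and (72 − 60)/60 = 20%, mean 25%. 90% pass within 28 days (SA2). Rate of low aPiMax 35%.

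**The plan's own figure.** 240 × 0.35 = 84, which matches SA2's n=84 and satisfies 'at least 80'. The protocol gives no events-per-variable rule for Aim 3; 80/9 = 8.9 and 84/9 = 9.3 are the implied values. The stated figure reproduces, on all 240 children.

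**Children with weaning-phase PRP and aPiMax at passage.**

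- If the 90% applies to all 240, then 240 × (0.90 − 0.25) = 156.
- If the 90% applies to the 180 who fail the first SBT, then 180 × 0.90 = 162.
- Most generous set, all 180 failures with a last available aPiMax: 180.

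**Events at 35% and variables at 8.9 events each.**

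| Analysis set | Children | Events | Variables |
|---|---|---|---|
| Acute-phase model | 240 | 84.0 | 9 (as stated) |
| Failed, later passed | 156 | 54.6 | 6.1 |
| Failed, later passed (other reading) | 162 | 56.7 | 6.4 |
| All who failed the first SBT | 180 | 63.0 | 7.1 (6.7 at 9.3) |

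Nine variables on 54.6 events would leave 54.6/9 = 6.1 events per variable.

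**What would restore 80 events.** A rate of 80/156 = 51%, 80/162 = 49% or 80/180 = 44%. Even all 216 children who ever pass an SBT would give only 216 × 0.35 = 75.6.

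**Sensitivity range (assumptions, not the expected result).** By age, the preliminary cohort in B.3.5 had rates, outside neonates, of 30% to 34%. At 30%, 156 children give 46.8 events (5.3 variables). The January 2023 entry in the final SAP sets a minimum of 230 enrolled, so 230 × 0.87 ≈ 200 evaluable. Then 200 × (0.90 − 0.25) = 130 children give 39.0 events at 30% and 45.5 at 35%. The acute-phase model has 60 events at 30% and 70 at 35%, also below 80.

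**The case against.** The strongest reply is that the arithmetic is sound: 35% of 240 is 84, and nine variables follows at about nine events each. That stands, and a reader who inferred a calculation error would be wrong. What is missing is the analysis set for the models that include weaning-phase PRP.

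It can also be said that children who fail the first SBT are probably weaker, so that 35% understates their rate. That is plausible, but the rate would have to reach 44–51%, and no section gives such a rate for eligible ages. Nor do first-SBT passers fill the gap. SAP Table 1 gives them a weaning length of about two hours, but the Aim 3 window begins at a failed SBT and aPiMax is measured before each SBT.

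Four stronger readings are tempting and should not be drawn:

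- **That about 39 events is the expected count.** It combines the lowest age-group rate with minimum enrolment, while the SAP's target is 230–276.
- **That 35% is too high for this trial.** The 30–34% comes from a mixed ventilated cohort measured just before extubation, and the age difference was not significant (p=0.12). This trial enrols hypoxemic parenchymal disease.
- **That the model explains an earlier aPiMax by later effort.** D.6.4.3 already pairs each window with its own aPiMax; only the model sentence omits the time point.
- **That the model is committed to nine or more covariates and is therefore overfitted.** The lists in A3 and D.6.4.3 are illustrative, and several items are secondary goals.

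The 8.9 is a back-calculated heuristic. SA2 implies about 216/20 = 10.8, and a stricter ratio only lowers the limit. Aim 3 is a secondary, observational aim; the primary comparison is untouched.

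**Conclusion.** The point holds as a sizing statement that covers one of the models it is attached to. At 240 evaluable children and 35%, the acute-phase model has 84 events and carries nine variables. A model containing weaning-phase PRP has 55–57 events and carries about six, and at most 63 events and 6–7 variables under the most generous set. No reading of the plan's own inputs brings it to 80.

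This assumes that the 35% rate applies equally to children who fail the first SBT, and it uses the implied 8.9 events per variable. The final SAP does not settle the matter: its outcome tables contain no model with PRP as the exposure, and it names Firth's method only for subgroup analyses. The correction is worth making, but it bears on a secondary aim only.

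**What to change.** In D.6.4.3, replace the single model and count with two:

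1. aPiMax at the first SBT on acute-phase PRP, in all children with a first SBT: 84 events and 9 variables at 240 evaluable; 70 events and 7 variables at 200, both at 35%.
2. aPiMax at SBT passage on weaning-phase PRP, adding acute-phase PRP if both are tested, in children who failed the first SBT only: about 55–57 events and about 6 variables. Specify a penalised fit (ridge or Firth) if more are kept.

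State the aPiMax time point for each multivariable outcome, and that no PRP window may end after the aPiMax it is used to explain. Say how children who never pass an SBT are handled; if a last available aPiMax is used, the ceiling is 63 events. Keep 35% as the planning rate, drop 'at least' from the rate, the event count and the variable count, and show 30–35% as a sensitivity range.

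The cost is protocol and SAP wording, plus a less favourable stated number of variables for the weaning model. No design, data collection or enrolment change is needed.
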